- d. To avoid multiple sticks drawing the blood samples for ketamine, norketamine and GABA at 90 minutes and 120 minutes after the start of the ketamine infusion, a second venous line will be placed.
- e. During the ketamine infusion, vital signs (blood pressure and heart rate) will be monitored as follows:
 - i. -5 minutes
 - ii. 0 (start of infusion)
 - iii. Post start of infusion: 5, 10, 15, 20, 25, 30, 35, and 40 minutes (end of infusion)

iv. Post end of infusion:

- 1. Every 5 minutes for remaining duration of the scan.
- 2. Blood pressure will continue to be obtained until there are two measurements at least 15 minutes apart that are within 10 mmHg of the baseline diastolic blood pressure or diastolic blood pressure is at least below 85.

During the ketamine infusion and MRI scans, the vital signs are obtained through an In Vivo® machine which displays in the room with the MRI scanner and physician who supervises the patient's medical state, and also displays in the operator's room on another console (where notes can be taken). The Research Assistant who remains in the operator's room during the infusion records the blood pressure and heart rate. After the subject is transferred back to the examination room, the blood pressure and heart rate will be obtained manually by the nurse.

- f. Intervention for Hypertension: If the systolic blood pressure increases to ≥ 200 or diastolic blood pressure increases to ≥115 mmHg during the ketamine infusion, the infusion will be permanently discontinued. The blood pressure will be monitored and if there is no decrease after 15 minutes, then:
 - i. One dose of sublingual nitroglycerine, 0.3 mg, will be administered.
 - ii. If there is no response within 10 minutes, clonidine 0.1 mg po will be administered every 30 minutes (total maximum dose 0.6 mg clonidine) until the desired blood pressure is reached. Desired blood pressure is defined as within normal range or 10 mmHg of baseline diastolic reading.
- g. If high blood pressure is symptomatic, i.e., blurred vision, headache, chest pain, the subject will be transferred to the ER. If they do not respond to the above treatment (f) then they will be transferred to the ER.

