- a. Subject responds to advertisement and completes a phone screen, approved under IRB #6879R-#5880R. If the subject appears eligible based on the phone screen, they will be scheduled for an in-person screening visit under Screening Protocol (IRB #6879R-#5880R) to determine whether inclusion/exclusion criteria (excluding medical screening) are met.
- b. Subject is given a detailed, verbal explanation of this study (IRB #6460) and IRB #4815 and given a copy of both consent forms.
- c. Subject gives written informed consent to participate in IRB #4815 and IRB #6460.
- d. Subject receives medical evaluation under IRB #4815 and an ECG under IRB #6460 to rule out exclusionary medical illnesses.
- e. At screening, subjects will complete the MADRS.

2. MRS and MRI Scanning:

_

- a. Subject will be informed that they should arrive to the clinic fasting (12 hours no food, 4 hours no liquids) prior to the ketamine infusion/MRI.
- b. We will obtain MRI scans before, and during, a slow intravenous infusion of saline solution with 0.5 mg/kg of ketamine hydrochloride (Abbott Laboratories, North Chicago, IL) over the course of approximately 40 minutes (see Figure 1).
- c. To avoid multiple sticks drawing the blood samples for ketamine, norketamine and GABA at 90 minutes and 120 minutes after the start of the ketamine infusion, a second venous line will be placed.

- d. During the ketamine infusion, vital signs (blood pressure and heart rate) will be monitored as follows:
 - i. -5 minutes
 - ii. 0 (start of infusion)
 - iii. Post start of infusion: 5, 10, 15, 20, 25, 30, 35, and 40 minutes (end of infusion)
 - iv. Post end of infusion:
 - 1. Every 5 minutes for remaining duration of the scan.
 - 2. Blood pressure will continue to be obtained until there are two measurements at least 15 minutes apart that are within normal range or 10 mmHg of the baseline diastolic blood pressure or diastolic blood pressure is at least below 85.

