During the ketamine infusion and MRI scans, the vital signs are obtained by an In Vivo® machine which displays in the room with the MRI scanner and physician who supervises the patient's medical state, and also displays in the operator's room on another console (where notes can be taken). The Research Assistant who remains in the operator's room during the infusion records the blood pressure and heart rate. After the subject is transferred back to the examination room, the blood pressure and heart rate will be obtained manually by the research assistant or nurse.

- e. Intervention for Hypertension: Same as above for patients.
- f. If high blood pressure is symptomatic, i.e., blurred vision, headache, chest pain, the subject will be transferred to the ER.
- g. Subjects will receive two MRI scans, one before and one during the administration of ketamine. MRI scans will be performed at the NYSPI MRI facility using the 3.0 Tesla GE scanner. The first measurement will consist of quantitative, structural MRI imaging for optimal segmentation of brain tissue into gray and white matter and cerebrospinal fluid. The second measurement will be the MR spectroscopy acquisition with GABA and glutamate spectroscopic editing. Patients will receive a structural and spectroscopy MRI scan lasting approximately 90 minutes. Structural scans will include T1-weighted images.

3. Follow up: At 3 and 6 months post-ketamine, all subjects we can contact will be evaluated to determine the absence of post-exposure ketamine use/abuse.

4. Withdrawal from Study:

_

Subjects will be withdrawn from the study if:

- a. They request it for any reason
- b. The PI judges that it is unwise to continue in the study, for example if the subjects are unable to comply with the study procedures and rules.
- c. A rise in systolic blood pressure \geq 200 mm Hg or diastolic blood pressure to \geq 115 mm Hg during the ketamine infusion.
- d. Other criteria for discontinuation will be appearance of symptoms meeting criteria for a psychiatric disorder according to DSM-IV criteria.

You can upload charts or diagrams if any

Criteria for Early Discontinuation

Criteria for Early Discontinuation

MDD Patients

Subjects will be withdrawn from the study if:

- a. They request it for any reason
- b. The PI judges that it is medically unwise to continue in the study, for example if the subjects are unable to comply with the study procedures and rules.

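### The rescue target for hypertension in Patients 5.f can be met on diastolic pressure alone, so an uncommon partial response can count as recovery with systolic still at 200 or above

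*Protocol*

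**What the plan says.** All references are to the protocol, Study Procedures.

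- **Start of the pathway (Patients 5.f).** Either component is enough: "If the systolic blood pressure increases to ≥ 200 or diastolic blood pressure increases to ≥115 mmHg during the ketamine infusion", the infusion stops for good.
- **First drug step (5.f).** "The blood pressure will be monitored and if there is no decrease after 15 minutes", one dose of sublingual nitroglycerine is given. The size of the decrease, and the component it refers to, are not stated.
- **Second drug step (5.f.ii).** "If there is no response within 10 minutes, clonidine 0.1 mg po will be administered every 30 minutes (total maximum dose 0.6 mg clonidine"). Dosing ends earlier if the target in the next item is met.
- **Target (5.f.ii).** "Desired blood pressure is defined as within normal range or 10 mmHg of baseline diastolic reading".
- **Transfer (5.g).** Symptomatic high pressure goes to the ER. For the rest: "If they do not respond to the above treatment (f) then they will be transferred to the ER".
- **End of routine readings, patients (5.e.iv.2).** Two measurements at least 15 minutes apart must be within "10 mmHg of the baseline diastolic blood pressure or diastolic blood pressure is at least below 85".
- **End of routine readings, volunteers (Healthy Volunteers 2.d.iv.2).** The measurements must be "within normal range or 10 mmHg of the baseline diastolic blood pressure or diastolic blood pressure is at least below 85".
- **Rescue for volunteers (2.e).** "Intervention for Hypertension: Same as above for patients". Step 2.f then restates the symptom transfer only.

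**The concern.** Systolic pressure can start the pathway, but no written rule requires it to recover before the pathway ends. No other part of the protocol gives a systolic recovery value. If systolic was the component that triggered rescue, the target can be reached without that component improving to any stated level.

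What is at stake is the safety of a subject in that position. It does not bear on allocation, blinding, endpoints or the analysis. A written target should not be able to declare recovery at the systolic level that stopped the infusion.

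**Working it through.** The protocol gives no figure to reproduce here. The check is whether one set of readings can meet the target while still meeting the trigger.

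**Conditions as written** (S, D = current systolic and diastolic; b = baseline diastolic)

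| Rule | Condition |
|---|---|
| Trigger, 5.f | S ≥ 200 or D ≥ 115 |
| Target, 5.f.ii | normal range, or D within 10 of b |
| End of readings, patients 5.e.iv.2 | D within 10 of b, or D < 85; two readings at least 15 min apart |
| End of readings, volunteers 2.d.iv.2 | normal range, or D within 10 of b, or D < 85; two readings at least 15 min apart |

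Even if normal range covers both components, it is joined by *or*, so the diastolic branch is sufficient. The patient rule for ending readings has no systolic term at all.

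**Illustrative case 1** (assumed pressures, not a predicted rate)

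1. Baseline 120/75, which is eligible (baseline pressure above 140/90 is excluded).
2. Trigger at 205/95: 205 ≥ 200.
3. Unchanged at 15 min, so nitroglycerine. Unchanged at 15 + 10 = 25 min, so first clonidine dose.
4. Then 200/84, no symptoms. 84 − 75 = 9 ≤ 10, so the target is met. 84 < 85 also meets the second branch for ending readings.
5. Systolic is 200 − 120 = 80 mmHg above baseline and still at the trigger.
6. Maximum clonidine is 0.6 / 0.1 = 6 doses, so 5 repeat doses (0.5 mg, over 5 × 30 = 150 min) are not called for.

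**Illustrative case 2** (baseline at the entry limit). Baseline 140/90, trigger at 210/118, later 202/100. 100 − 90 = 10, so the diastolic branch is met with systolic 202 ≥ 200.

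**How narrow the gap is.** Take S = 200. The least pulse pressure that meets the diastolic branch of 5.f is 200 − (b + 10). For the diastolic-only limbs of the rules ending readings it is 200 − max(84, b + 10), with below 85 taken as 84.

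| Assumed b | 5.f diastolic branch | Rules ending readings |
|---|---|---|
| 60 | 200 − 70 = 130 | 200 − 84 = 116 |
| 75 | 200 − 85 = 115 | 200 − 85 = 115 |
| 90 | 200 − 100 = 100 | 200 − 100 = 100 |

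The gap therefore needs a wide pulse pressure, at least 100 mmHg in every case shown.

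**Does 5.g close it?** It catches a patient whose pressure is unchanged after the regimen. A partial response is different: *respond* is undefined, and the only end-point in 5.f is the target itself, which the subject in case 1 has met. Transfer is then not clearly required.

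**The case against.** The strongest case against has four parts.

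1. **No practical effect now.** The continuation form (Application for Continuation of Research, Status) reports that interventions are finished and only analysis continues. This stands, and it limits the point to re-use of the procedures.
2. **The scenario is uncommon.** It needs the pulse pressures above in subjects screened for hypertension and cardiovascular history. Section 5.2 describes the pressure rises in 11 earlier patients at 0.5 mg/kg as modest and largely resolved by 75 minutes. This stands and bears on severity, but not on whether the rule is written correctly.
3. **Other safeguards exist.** The infusion stops on either component and an ACLS-certified physician is present. Symptoms lead to the ER, and reaching the trigger means withdrawal (Patients 7.d, Healthy Volunteers 4.c). Patients 7.e leaves room for clinical judgement on deterioration. These are real protections, but none sets a systolic recovery value.
4. **Choosing diastolic as the recovery marker is a medical decision.** The exact limit is indeed for the medical team. But the protocol makes systolic a trigger in its own right, so leaving it out of the target is a mismatch within the text.

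Three stronger readings are tempting, and the protocol does not support them.

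- *Required monitoring ends for the subject in case 1.* The rule ending readings sits in 5.e, the routine schedule. 5.f has its own instruction to monitor, with no stated end, and 5.e.iv.1 keeps five-minute readings going until the scan ends. Whether 5.e.iv.2 also releases a subject treated under 5.f is not stated.
- *A patient who does not improve at all has no next step.* On its ordinary reading, 5.g sends that patient to the ER.
- *A volunteer who does not respond has no next step.* 2.f omits the non-response transfer, but 2.e adopts the patient intervention and can fairly be read to bring 5.g with it. This is a point to clarify and not an established gap.

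**Conclusion.** The point holds as a minor defect in a written safety rule. The clonidine target in 5.f, and the routine rules ending readings in 5.e.iv.2 and 2.d.iv.2, can be met on diastolic alone although systolic can start the pathway. In a partial response without symptoms, the target is met with systolic still at 200 or above, and 5.g does not clearly require transfer.

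The logic rests on the wording alone. The pressures in the cases are assumed, and the protocol gives no basis for a rate. Nothing in it shows that any participant was in this position or came to harm. Trial results are not affected.

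**What to change.** For any re-use of these procedures:

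- In 5.f, 5.e.iv.2 and 2.d.iv.2, require both systolic and diastolic to return to the normal range or to within a stated margin of their own baselines. For example, use 10 mmHg for diastolic and a systolic margin set by the medical team. A target of merely below 200 would be too weak. With a baseline systolic of at most 140 (the entry limit), any margin under 200 − 140 = 60 mmHg keeps the target below 200, and the chosen limit should sit well below that level.
- In 5.g, define *respond* as reaching that target.
- State whether 5.e.iv.2 governs the end of monitoring for a subject treated under 5.f.
- As a clarification only, state that 2.e for volunteers includes the 5.g non-response transfer.

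The cost is a few changes of wording. No new measurement is needed, since systolic comes with each blood pressure reading. The downside is that some subjects are observed or treated longer. In case 1 that is at most five further clonidine doses over 150 minutes, with the sixth dose at 15 + 10 + 150 = 175 min after the trigger, and then transfer if the target is still not reached.

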5.1. Drug-free interval

We will recruit inpatients or outpatients with a major depressive episode. Patients are generally referred by their own physician or from a clinic. Medication washout is performed as an inpatient at the 4-Center or 5-South or as an outpatient by a psychiatrist in the Department of Molecular Imaging and Neuropathology. At a minimum, outpatients will be monitored weekly in person and on the telephone during the washout period. In addition, there is 24-hour coverage for emergencies by the Molecular Imaging and Neuropathology on-call physician. Only patients who currently have failed an adequate trial for their illness will be tapered off these medications. For example, patients on sub-therapeutic doses of antidepressants or in the early phase of an antidepressant trial will not be tapered, rather they will be referred back to the treating clinician with a recommendation to complete an adequate trial of medicine.

There is a risk that drug washout will result in a worsening of the patient's condition. If the responsible physician (inpatient or outpatient) determines that treatment cannot be delayed safely or the patient withdraws from the study, all necessary treatment is offered. Patients are offered up to 3mg of Ativan \leq 2 times a week to relieve some symptoms during this phase. Ativan will be stopped for the 24 hours prior to scanning.

If the subject clinically deteriorates in the course of the drug washout to the extent that they feel they cannot tolerate the washout, or they are observed objectively to become significantly more depressed or develop suicidal ideation such that admission to hospital or medication is required clinically, we will drop them from the protocol and commence immediate appropriate treatment. In carrying out these studies over the last 10 years in depressed inpatients, many of whom were highly suicidal, no patient has completed suicide and only one patient attempted suicide during the medication washout period.

5.2. Side Effects of intravenous ketamine

Risks of ketamine injection include both medical and psychiatric or behavioral risks.

Medical risks

Administration of sub-anesthetic doses of ketamine I.V. may induce a modest rise in blood pressure. We have administered sub-anesthetic doses of ketamine I.V. (0.5mg/kg over 40 minutes) in the setting of a currently approved MRI/MRS brain imaging protocol at this institution (IRB #5786, PI: [name]). The resulting effects on vital signs for the eleven patients scanned under protocol #5786 are presented as a function of time in Table 1 below for the duration of the ketamine injection. These modest increases all peaked and largely resolved by 75 minutes, with vitals returning to near baseline.

Specific measures and precautions

Any medical risks from increased blood pressure will be minimized through the careful screening of potential subjects. Subjects will be excluded for baseline hypertension or any history of cardiovascular illness. In addition, an ACLS certified physician, [name], [name] **or** [name] or [name], will be present during the procedure. Nausea and vomiting will be treated supportively and, if severe, with anti-emetic agents; if necessary, administration of ketamine will be discontinued. Subject will be informed that they should be fasting (12 hours no food, 4 hours no liquids) prior to the ketamine infusion/MRI. For these reasons, the medical risks involved in participation in this study will be minimized.

Table 1. Effects of ketamine on systolic and diastolic blood pressure in a group of patients (n=11). The dose of ketamine was 0.5 mg/kg given over 40 minutes.

Time (min)	Systolic Blood Pressure during Ketamine (mm Hg)	Diastolic Blood Pressure during Ketamine (mm Hg)	Pulse during Ketamine (min ⁻¹)
0	111	70	69
5	113	72	63
10	116	73	69

Psychiatric or behavioral risks

Ketamine is an FDA-approved dissociative anesthetic. Ketamine exposure at the sub-anesthetic dose to be used in this study can be associated with a moderate dissociative state, which is well tolerated in the majority of cases and spontaneously reversible. There is extensive clinical experience with ketamine used at anesthetic doses and no long-term detrimental effects of ketamine exposure have been reported. It is possible that ketamine administration will increase the risk of psychosis, even in normal subjects. Ketamine is a street drug of abuse, sometimes called 'special k.' As such, it poses the risk that exposure during this study may predispose subjects to subsequent abuse of this drug. For this reason, a careful history of any past or present problems with substance abuse will be obtained on screening and any such positive history will constitute an exclusion criterion. Moreover, we will follow patients while they are on open treatment and review any evidence of abuse that may appear after the ketamine infusion.

Specific measures and precautions

The experiment will be carried out in the presence of at least one psychiatrist. Severe agitation or hyperarousal will be treated with intravenous benzodiazepine (lorazepam) or neuroleptics, as indicated. The risks of exposing subjects to a drug of abuse potential will be minimized by explaining this risk to prospective subjects, and by excluding from the study any subjects with documented or suspected prior substance or alcohol dependence history. Any subjects requiring admission due to any possible adverse outcomes related to the administration of ketamine will be cleared by a physician for discharge from either 4-Center or 5-South the morning after ketamine administration.

5.3. Intravenous catheters

There is a small risk of infection and bleeding associated with intravenous catheters, which are prevented by proper techniques. Placement of IVs will be by a physician or nurse.

5.4. Blood sampling

Adverse effects of blood sampling will be minimized by exclusion of subjects with low hemoglobin levels during screening (Hemoglobin ≤ 12 g/dl in men and ≤ 11 g/dL in women).

5.5. Discomfort during scanning

It may be uncomfortable to lie motionless in the scanner (MRI) and it may cause some subjects to feel anxious. Our staff will be available to provide support, reduce anxiety, optimize the comfort of the subject and remove the subject from the machine if requested.

5.6. MRI scanning

While there have been no reports of any long-term ill effects caused by magnets of the same or even higher strength, the long-term effects of being placed in a magnet of this strength (3 Tesla) are unknown. The MRI scanner uses a large magnet to take pictures of the brain and is not associated with any known medical risks, except for persons who have a heart pacemaker, or have metal in their body (e.g. shrapnel or surgical prostheses) which may be affected by the magnet. Patients will be asked to notify us if this is the case. There is also the risk of burns from medicinal patches during the MRI; therefore, subjects will be asked to remove any patches prior to the scanning session. Also, although there are no known risks associated with pregnancy, we will not scan anyone who is pregnant. Therefore, for women of childbearing years, pregnancy testing will be conducted the day of the MRI. Some people have reported sensations during the MRI scan such as "tingling" or "twitching" (or, very rarely a painful sensation), which are caused by changes in the magnetic field that can stimulate nerves in your body. If the subject experiences sensations and feels uncomfortable, the MR technologist will stop the scan immediately. Occasionally, some people experience nervousness or claustrophobic feelings due to the scanner's small space. Despite these sensations, in our experience, no one has had sensations from the scanning that did not stop as soon as the scanning stopped. The MRI scan is not painful, but having to lie still in the enclosed space of the scanning table is uncomfortable for some people.

5.7. Pregnancy

Women of child-bearing age will be required to have a urine pregnancy test administered at the time of initial screening as well as within 24 hours prior to the MRI scan. Subjects will not be charged for the pregnancy test. They are excluded partly because of unknown risk to the fetus and because lying in the scanner may be difficult and there may be biological effects on the brain of fetus.

5.7. Electrocardiogram

An electrocardiogram has no serious risks. On rare occasions a rash may develop where the electrodes are places which usually resolves without treatment.

6. Describe benefits to subjects, if any.

Subjects will receive a complete medical, neurological and psychiatric evaluation, results of which will be communicated to them. Subjects are not expected to benefit directly from participation in this study; however, the results of the MRI will be shared with the subject and/or a physician of their choice. Because this MRI scan is being performed for research purposes only it may not show problems that would normally

be found in a typical clinical, diagnostic MRI scan ordered by a doctor for a specific medical problem.

7. Confidentiality: Describe means by which privacy will be protected and confidentiality of data maintained. Include procedures for the storage and protection of electronic data. NOTE: If a Certificate of Confidentiality will be obtained for this study, please indicate.

Once a subject enrolls in the project they are given a code number, which is used for all subsequent data and/or lab forms. The code list and subject names as well as all data are kept in locked files with access limited to those directly responsible for maintenance of these files by the research team or institutional personnel as part of a routine audit.

The MRI report will be maintained as part of the clinical database at the New York State Psychiatric Institute along with the subject's name and will be accessible to clinicians. For patients (only), their psychiatric diagnosis will not be part of the report. All subjects will receive feedback about their scans. All results will be shared with research subjects in a manner that is consistent with the acuity and certainty of the finding, and will be communicated by an appropriately qualified member of the research team in the form of a letter approved by the IRB and will be contacted by telephone if there is evidence of an abnormality. Results will be shared with the subject or a physician designated by the subject.

Methods to Protect Confidentiality

Describe methods to protect confidentiality

Once a subject enrolls in the project they are given a code number, which is used for all subsequent data and/or lab forms. The code list and subject names as well as all data are kept in locked files with access limited to those directly responsible for maintenance of these files by the research team or institutional personnel as part of a routine audit.

The MRI report will be maintained as part of the clinical database at the New York State Psychiatric Institute along with the subject's name and will be accessible to clinicians. For patients (only), their psychiatric diagnosis will not be part of the report. All subjects will receive feedback about their scans. All results will be shared with research subjects in a manner that is consistent with the acuity and certainty of the finding, and will be communicated by an appropriately qualified member of the research team in the form of a letter approved by the IRB and will be contacted by telephone if there is evidence of an abnormality. Results will be shared with the subject or a physician designated by the subject. Will the study be conducted under a certificate of confidentiality?

Direct Benefits to Subjects

Direct Benefits to Subjects

Subjects will receive a complete medical, neurological and psychiatric evaluation, results of which will be communicated to them. Subjects are not expected to benefit directly from participation in this study; however, the results of the MRI will be shared with the subject and/or a physician of their choice. Because

this MRI scan is being performed for research purposes only it may not show problems that would normally be found in a typical clinical, diagnostic MRI scan ordered by a doctor for a specific medical problem.

Compensation and/or Reimbursement

Will compensation or reimbursement for expenses be offered to subjects?

Yes

Please describe and indicate total amount and schedule of payment(s).

Include justification for compensation amounts and indicate if there are bonus payments.

Subjects will receive \$150.00 for completion of the MRI/MRS scans and the ketamine infusion, \$50 for the baseline evaluation, and \$50 for the post-treatment assessments, for a total of \$250. For non-responders that elect to undergo a second infusion, there will be not be any compensation for the second infusion.

References

References

- 2. Dakwar E, et al. The effects of subanesthetic ketamine infusions on motivation to quit and cue-induced craving in cocaine-dependent research volunteers. *Biol Psychiatry*. Jul 2014; 76(1):40-46.

Uploads

Upload the entire grant application(s)
Upload copy(ies) of unbolded Consent Form(s)
Upload copy(ies) of bolded Consent Form(s)
Upload copy(ies) of the HIPAA form
6460_HIPAA_9_23_15.pdf
Upload any additional documents that may be related to this study
6460_ACAR_2015_recruitment_demo_final_Sheet1.pdf

Patients

Ethnic Category		Sex/Gender	
	Females	Males	Total
Hispanic or Latino	4	3	7
Not Hispanic or Latino	29	21	50
Unknown (individuals not reporting ethnicity)	0	0	0
Ethnic Category: Total of All Subjects*	33	24	57
Racial Categories			
American Indian/Alaska Native	0	0	0
Asian	2	4	6
Native Hawaiian or Other Pacific Islander	0	0	0
Black or African American	1	6	7
White	27	11	38
More Than One Race	3	1	4
Unknown or Not Reported	0	2	2
Racial Categories: Total of All Subjects*	33	24	57

Controls

Ethnic Category		Sex/Gender	
	Females	Males	Total
Hispanic or Latino	1	0	1
Not Hispanic or Latino	6	6	12
Unknown (individuals not reporting ethnicity)	0	0	0
Ethnic Category: Total of All Subjects*	6	6	12
Racial Categories			
American Indian/Alaska Native	0	0	0
Asian	0	0	0
Native Hawaiian or Other Pacific Islander	0	0	0
Black or African American	2	3	5
White	2	4	6
More Than One Race	2	0	2
Unknown or Not Reported	0	0	0
Racial Categories: Total of All Subjects*	6	7	13
